2.2.2. Clinical Pharmacokinetics

Single (up to 1,500 mg) and multiple ascending oral doses of GLPG1690 (up to 1,000 mg q.d.) for 14 days were assessed in healthy male subjects under fed conditions. GLPG1690 was rapidly absorbed with a median time to maximum plasma concentration (t_{max}) of 0.5-2 h. Steady state exposure of GLPG1690 increased approximately in proportion with the dose between 300 to 1,000 mg total daily. Excretion of unchanged GLPG1690 in human urine was low (<1.8% in 24 hours [h] based on unchanged GLPG1690) and rapid. There was no impact on the urinary 6β -OH-cortisol/cortisol ratio after repeated dosing suggesting a lack of CYP3A4 induction by GLPG1690.

The PK of GLG1690 was similar between Caucasian and Japanese healthy male subjects. The PK of GLPG1690 in subjects with IPF was not markedly different from those observed in healthy subjects at the same dose level.

Food decreased the rate of absorption of GLPG1690 given as tablet (as expected by delay in gastric emptying), but there was no clinically relevant difference in the bioavailability of GLPG1690. A higher between-subject variability was observed in fasted state, with 4 subjects out of 12 having 5- to 10-fold lower exposure than the other subjects. The rate of elimination was not impacted by food. The mean terminal half-life ($t_{1/2}$) after a single 600 mg dose as tablets was approximately 11 h.

After q.d. dosing with the strong CYP3A4/potent P-gp inducer rifampin (600 mg q.d.) for 10 days, GLPG1690 (600 mg) exposure was decreased (by 6.0- and 9.3-fold for maximum observed plasma concentration (C_{max}) and area under the plasma concentration-time curve from time 0 to 24 h [AUC_{0-24h}], respectively) without any significant change in the apparent rate of elimination.

Exposure of GLPG1690, as measured by area under the concentration-time curve from time 0 to infinity ($AUC_{0-\infty}$), was 3- and 4-fold greater when administered in combination with itraconazole and voriconazole, respectively, than when GLPG1690 was administered alone. Maximum exposure (C_{max}) of GLPG1690 increased slightly following administration of GLPG1690 in combination with itraconazole or voriconazole compared with administration of GLPG1690 only (C_{max} values were 1.4-fold greater following administration in combination with itraconazole or voriconazole). This increase is unlikely to be clinically significant. GLPG1690 can therefore be classified as a moderately sensitive substrate of CYP3A4 as it demonstrated an increase in AUC of ≥ 2 to <5-fold with strong index inhibitors. Comparison of the plasma profiles showed no impact on the apparent rate of elimination of GLPG1690.

The potential impact of GLPG1690 600 mg on the PK of single doses of pirfenidone and nintedanib was evaluated. Exposure of pirfenidone and its metabolite 5-carboxypirfenidone, as measured by C_{max} , $AUC_{0-\infty}$, and terminal elimination half-life ($t_{1/2}$) was not affected when administered in combination with GLPG1690, compared to when pirfenidone was administered alone. Exposure of nintedanib, as measured by C_{max} , $AUC_{0-\infty}$ was approximately 2-fold greater when administered in combination with GLPG1690, than when GLPG1690 was administered alone. Nintedanib $t_{1/2}$ was not affected by coadministration of GLPG1690.

As described in Section 2.2.1, the additional study GLPG1690-CL-113 evaluated the effect of multiple oral doses of GLPG1690 on the PK of nintedanib 150 mg b.i.d. (the indicated dose in the prescribing information) under different dosing conditions (GLPG1690 dose and time of GLPG1690 dose versus the nintedanib morning dose).

As observed in the previous GLPG1690-CL-109 study, when GLPG1690 was administered at the same time as the morning dose of nintedanib, an interaction was again observed, i.e., the nintedanib exposure was increased when administered in combination with GLPG1690 compared to nintedanib alone. The magnitude of the effect on nintedanib exposure was dependent on the dose of GLPG1690 (200 mg or 600 mg once daily [q.d.]) and time difference between nintedanib and GLPG 1690 administration.

When GLPG1690 200 mg was administered at the same time as the morning dose of nintedanib, the maximum observed plasma concentration after the morning nintedanib dose ($C_{\max 0-11}$) increased from [REDACTED] (nintedanib administered alone) to [REDACTED] and the area under the plasma concentration-time curve after the morning nintedanib dose (AUC_{0-11}) increased from [REDACTED] respectively. With GLPG1690 600 mg, the increase in nintedanib $C_{\max 0-11}$ was from [REDACTED] (nintedanib administered alone) to [REDACTED] and in AUC_{0-11} from [REDACTED]

When the 600 mg GLPG1690 dose was administered 2 hours and 4 hours later than the morning dose of nintedanib, the interaction was decreased as compared to when administered concomitantly. With the 2-hour interval the increase in nintedanib $C_{\max 0-11}$ was from [REDACTED] and in AUC_{0-11} from [REDACTED]. With the 4-hour interval the increase in nintedanib $C_{\max 0-11}$ was from [REDACTED] and in AUC_{0-11} from [REDACTED]

Similarly, when the 200 mg GLPG1690 dose was administered 2 hours later than the morning dose of nintedanib, the increase in nintedanib $C_{\max 0-11}$ was from [REDACTED] and in AUC_{0-11} from [REDACTED]

2.2.3. Clinical Pharmacodynamics

After a single administration of GLPG1690, a significant dose-dependent percentage reduction of LPA C18:2 was observed in plasma. This effect started from 0.5 hours after IMP intake, reached a plateau, and was sustained over time up to 24 hours after IMP intake. Multiple q.d. or b.i.d. ascending doses resulted in a similar effect on LPA C18:2. A strong reduction in LPA C18:2 levels was already observed at Day 14 before IMP intake, pointing to a sustained effect over 14 days.

The sustained effect on LPA C18:2 was also confirmed by area under the effect-time curve for the percentage reduction from baseline and maximum effect (expressed as a percentage reduction from baseline) (E_{\max}).

GLPG1690 induced a fast and sustained reduction in plasma LPA C18:2 levels in subjects with IPF, indicative for target engagement. At the follow-up visit, the mean LPA C18:2 level was back to baseline levels, indicating that the inhibitory effect of GLPG1690 on the target is reversible. The profiles of plasma LPA C18:2 levels after single doses of pirfenidone or nintedanib whether administered alone and in combination with multiple doses of GLPG1690 were similar over time.

3. CLINICAL STUDY OBJECTIVES

3.1. Primary Objective

- To evaluate the efficacy of two doses of GLPG1690 in addition to local standard of care compared to placebo in subjects with IPF as evaluated by the rate of decline of FVC over a period of 52 weeks

3.2. Secondary Objectives

3.2.1. Key Secondary Objectives

- To evaluate the impact of two doses of GLPG1690 in addition to local standard of care compared to placebo in subjects with IPF on:
 - disease progression defined as deterioration of FVC or all-cause mortality at 52 weeks
 - respiratory-related hospitalization until the end of the study
 - changes in quality of life (measured by St. George's Respiratory Questionnaire [SGRQ] total score) at 52 weeks

3.2.2. Other Secondary Objectives

- To evaluate the efficacy of two doses of GLPG1690 in addition to local standard of care compared to placebo in subjects with IPF as evaluated by the rate of decline of FVC until the end of the study
- To evaluate the impact of two doses of GLPG1690 in addition to local standard of care compared to placebo in subjects with IPF on:
 - disease progression defined as deterioration of FVC or all-cause mortality until the end of the study
 - changes in quality of life (measured by SGRQ total score) until the end of the study
 - all-cause non-elective hospitalization until the end of the study
 - respiratory-related mortality until the end of the study
 - lung transplant until the end of the study
 - acute IPF exacerbation until the end of the study
 - all-cause mortality or lung transplant until the end of the study
 - all-cause mortality, or lung transplant, or qualifying for lung transplant until the end of the study
 - all-cause mortality, deterioration of FVC, or respiratory-related hospitalization until the end of the study
 - all-cause mortality or respiratory-related hospitalizations until the end of the study
- To evaluate the effect of two doses of GLPG1690 in addition to local standard of care compared to placebo on the changes from baseline in FVC at 52 weeks and until the end of the study
- To evaluate the safety and tolerability of two doses of GLPG1690 in addition to local standard of care compared to placebo until the end of the study
- To evaluate changes compared to placebo in subjects with IPF in:

- cough-related quality of life (measured by the Leicester Cough Questionnaire [LCQ] and by the Visual Analogue Scale [VAS] Cough and Urge to Cough) at 52 weeks and until the end of the study
 - quality of life (measured by EuroQOL 5-Dimensions Questionnaire [EQ-5D] and King's Brief Interstitial Lung Disease [K-BILD] total score and domains over time) at 52 weeks and until the end of the study
- To evaluate the PK of GLPG1690, pirfenidone, and nintedanib (as appropriate) in subjects with IPF at 52 weeks and until the end of the study
 - To evaluate the effect of two doses of GLPG1690 in addition to local standard of care compared to placebo in subjects with IPF on the changes in functional exercise capacity measured by the 6-Minute Walk Test (6MWT) at 52 weeks and until the end of the study
 - To evaluate the effect of two doses of GLPG1690 in addition to local standard of care compared to placebo on the diffusing capacity of the lung for carbon monoxide (DLCO) at 52 weeks and until the end of the study

3.3. [REDACTED]

[REDACTED]

[REDACTED]

[REDACTED]

[REDACTED]

[REDACTED]

[REDACTED]

4. INVESTIGATIONAL PLAN

4.1. Clinical Study Design

This clinical Phase 3 study is a randomized, double-blind, parallel-group, placebo-controlled multicenter study designed to evaluate the efficacy and safety of two doses (200 mg q.d. and 600 mg q.d.) of orally administered GLPG1690 in addition to local standard of care for at least 52 weeks in adult subjects with a centrally confirmed diagnosis of IPF. Local standard of care for IPF is defined as receiving either pirfenidone or nintedanib at a stable dose for at least two months before screening, and during screening; or neither pirfenidone or nintedanib (for any reason). A stable dose is defined as the highest dose tolerated by the subject during those two months. A total of approximately 750 subjects with confirmed diagnosis of IPF will be randomized, 250 subjects in each treatment group (GLPG1690 600 mg q.d., GLPG1690 200 mg q.d., or matching placebo).

The diagnosis of IPF will be confirmed by central reading of the chest high-resolution computed tomography (HRCT) and by central review of the available lung biopsy (LB), if required, based on the Fleischner White Paper [15] as described in Section 6.3 and Appendix 1.

A schematic diagram of the clinical study design, procedures, and stages is provided in [Figure 1](#).

[figure not shown]

Figure 1: Schematic Study Overview

D=Day, EoST/EoSA=end of study treatment/end of study assessments, FU=follow-up, V=Visit, W=Week.

Enrolled subjects will come to the clinical study center at screening (two visits from Day -28 to Day -1). Visit 2 of screening can only take place after confirmed IPF diagnosis on HRCT and LB (if applicable) (for details, refer to Section 6.3 and Appendix 1).

For the in- and exclusion criteria, please refer to Section 4.5.1 and Section 4.5.2, respectively.

At Visit 3, eligible subjects will be randomized in a 1:1:1 ratio to receive GLPG1690 600 mg q.d., GLPG1690 200 mg q.d., or matching placebo for at least 52 weeks. Randomization will be stratified for background local standard of care for treatment of IPF.

Subjects will come to the clinical study center on Day 1 (baseline), Weeks 2, 4, 8, 12, 18, 26, 34, 42, 52, and every 12 weeks thereafter. Additional unscheduled visits are allowed if, in the investigator's opinion, further evaluation (clinical, laboratory, or other) is needed.

When the last subject reaches 52 weeks (Visit 12), subjects still taking IMP and who had a scheduled visit at the clinical study center within 6 weeks before this date will be contacted by their investigator (phone call) to discontinue IMP within 7 days after this date. Then the last scheduled visit will be documented as the end of study treatment (EoST) visit. These subjects will be invited to their follow-up visit scheduled at the clinical study center 4 weeks after their last dose of IMP (± 7 days). For subjects still taking IMP and who had their last scheduled visit more than 6 weeks before the date that the last subject reaches 52 weeks into the study (Visit 12), a scheduled visit will be planned within 2 weeks of this date for an EoST visit, followed by a follow-up visit 4 weeks later (visit at clinical center or phone call). Note that these subjects will continue IMP intake until their EoST visit.

For subjects who, for any Coronavirus disease (COVID-19)-related reason, cannot perform study procedures, extended visit windows, the possibility to conduct phone/televisits and home (or other remote location) visits, and alternative assessment procedures are detailed in Section 6.1.1.

Subjects who discontinue IMP early (early treatment discontinuation [ETD]), with the exception of patients lost to follow-up and patients who withdraw consent, will be encouraged to complete all following visits and evaluations as originally planned per protocol.

In particular, the subject will be requested if at all possible to attend:

- the first scheduled visit after their Early Treatment Discontinuation (ETD)
- The Week 26 visit (if not done before IMP discontinuation)
- the Week 52 visit (if not done before IMP discontinuation)
- after Week 52, visits every 24 weeks up to End of Study Assessments (EoSA), as described in Section 6.11.2

For procedures in case of ETD, refer to Section 4.5.4. In the exceptional case that a clinical study center visit cannot be attended, a phone call by the investigator will be made to evaluate safety, in combination with scheduled clinical study center visits.

Each subject will have a screening period of maximum 28 days. The duration of study treatment for individual subjects will vary from 52 weeks for the last enrolled subject to e.g. 132 weeks for the first enrolled subject (assuming a recruitment period of 80 weeks, the actual duration will depend on the actual time to recruit subjects for the study). A follow-up visit (at the clinical study center or by phone call, decided by the investigator) is planned 4 weeks after the EoST/end of study assessment (EoSA) visit.

At the end of this study, treatment with IMP in an optional extension study (under a separate study protocol) may be offered to all eligible subjects, provided Independent Ethics Committee (IEC)/Institutional Review Board (IRB) and Competent Authority approvals for such an extension are granted.

To protect the safety and integrity of the study data, an independent data monitoring committee (IDMC) will be implemented, as well as a clinical endpoint adjudication committee (CEAC). Charters are in place for all committees. For additional information, refer to Sections 8.1 (for IDMC) and 8.2 (for CEAC).

For detailed information regarding dosage form, packaging, and labeling of the IMP, please refer to Sections 5.2 and 5.3.

4.1.1. Definition of End of Trial

The global end of trial will be reached when the last subject has completed the last follow-up visit (scheduled clinical study center visit or phone call), i.e. four weeks (± 7 days) after the end of study treatment (EoST) or end of study assessments (EoSA) visit (Section 4.1 and Section 6.11.2).

4.1.2. Guidance for dose modification in case of adverse events

At any stage, the investigator can decide to permanently discontinue IMP for concerns regarding safety and tolerability, i.e. an AE including clinically significant abnormal laboratory tests. For abnormal liver function tests (LFTs), specific guidance is described in Appendix 9.

For the subsequent management of these AEs, the investigator can reduce the dose, interrupt, or permanently discontinue the IMP. Down-titration will be a one-step process to the lowest reduced dose. Once the AE has stabilized or improved, the dose can be increased again (re-escalation). For the re-escalation from the lowest reduced dose, an intermediate reduced dose level is required (Figure 2).

[figure not shown]

Figure 2: Study Drug Dose Modification: Down-titration and Re-escalation Steps

Tablet colors are for illustration purposes only

For all AEs, the investigator is advised to evaluate the concomitant medication, including local standard of care for the treatment of IPF, as part of the benefit-risk evaluation. The recommended duration of a different dose level or interruption for elevated LFTs is at least 2 weeks.

Elevated LFTs

At Visit 3 (randomization visit), blood samples are collected before IMP intake and the results of the laboratory tests will only be known after IMP intake. Therefore, if the LFTs are abnormal at this visit, the investigator needs to discontinue IMP (only if aspartate aminotransferase [AST] or alanine aminotransferase [ALT] $\geq 1.5x$ upper limit of normal [ULN], total bilirubin $\geq 1.5xULN$, and/or gamma glutamyl transferase [GGT] $\geq 3xULN$). It is recommended to consult the contract research organization (CRO) medical monitor (as per study contact list) or sponsor's study physician (if the former is not available).

At any visit from Visit 4 onwards:

Continue as planned: AST or ALT $\geq 1.5x$ to $3xULN$.

Discontinuation of IMP:

- AST or ALT >8xULN: permanently discontinue IMP with close observation*.
- AST or ALT \geq 3xULN with signs or symptoms of severe liver damage**: permanently discontinue IMP with close observation*.
- AST or ALT \geq 3xULN for more than 2 weeks
- AST or ALT \geq 3xULN during re-escalation (described below)

Down-titration to reduced dose level or interruption of IMP:

- AST or ALT \geq 3x to 5xULN without signs of severe liver damage**:
Down-titrate to low (reduced) dose level or interrupt IMP for at least 2 weeks (to be decided by the investigator, based on the subject's risk assessment).
- AST or ALT \geq 5x to 8xULN without signs of severe liver damage**:
Interrupt IMP for at least 2 weeks.

During these periods of at least 2 weeks: Re-test AST, ALT, alkaline phosphatase, total bilirubin, and eosinophils within 48 to 72 hours, approximately at 7 days, thereafter approximately at 14 days, and also assess signs of severe liver damage**. If local regulations allow, home visits can be performed if subjects cannot come to the clinical study center.

Re-escalation after each period of at least 2 weeks at any dose level:

- Remain on the highest tolerated dose at investigator's discretion. Monitoring of LFTs can return to the planned study assessments once the LFTs have stabilized at the highest tolerated dose level for 8 weeks.
- AST and ALT <3xULN:
Re-escalate to the next dose level for at least 2 weeks, with regular LFT monitoring (weekly for the first 2 weeks, biweekly for the following weeks, or more frequently at investigator's discretion) and repeat re-escalation to next higher dose level every 2 weeks (or longer at investigator's discretion) if AST and ALT <3xULN.
- AST or ALT \geq 3xULN:
Discontinue IMP.

*Close observation is defined as:

- Monitor two to three times per week all of the following parameters: ALT, AST, alkaline phosphatase, total bilirubin, eosinophils, and International Normalized Ratio (INR). If local regulations allow, home visits can be performed if subjects cannot come to the clinical study center.
- Frequency of retesting can be reduced to once a week or less if abnormalities stabilize or the IMP has been discontinued; however, monitoring might still be needed more frequently taking into consideration the standard of care and/or changes to this.
- Re-query history of symptoms, prior and concurrent diseases, concomitant medication and non-prescription medicines, herbal, dietary supplements, alcohol use, recreational drug use, special diets.
- Rule out all of the following: acute viral hepatitis, auto-immune hepatitis, alcoholic hepatitis, non-alcoholic fatty hepatitis, hypoxic/ischemic hepatitis, biliary tract disease, and cholestasis.
- Re-query exposure to environmental chemical agents.

– Consider gastro-enterology or hepatology consultations.

** Signs of severe liver damage:

- Increase of liver transaminases is accompanied by appearance of fatigue, nausea, vomiting, right upper abdominal quadrant pain or tenderness, fever, rash and/or eosinophilia (>5%), and/or
- Total bilirubin ≥ 1.5 x ULN, or
- INR >1.5.

Each blinded treatment kit will have blisters for the high (original) dose level, intermediate (reduced) dose level, and low (reduced) dose level, allowing the clinical study center to modulate the IMP dose for a particular subject, even without knowing the original treatment allocation (also see Section 5.2).

The Investigator will be responsible for managing COVID-19 infected subjects and the decision to continue or interrupt IMP for subjects with confirmed or suspected cases of COVID-19 infection is at the investigator's discretion. Guidance on continuation of IMP and requirements for assessments conducted during the COVID-19 pandemic are provided in Section 6.1.1.

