APPENDIX 9: ALGORITHM FOR ELEVATED LIVER FUNCTION TESTS

	AST or ALT increase to				
	≥1.5x to 3xULN	≥3x to 5xULN	≥5x to 8xULN	≥3xULN with signs of severe liver damage ¹	≥8xULN
Visit 1 (screening)	Not eligible	Not eligible	Not eligible	Not eligible	Not eligible
Visit 3 (randomization)	Discontinue IMP ²	Discontinue IMP ²	Discontinue IMP ²	Discontinue IMP ²	Discontinue IMP ²
From Visit 4 onwards	Continue as planned	Down-titration: reduce or interrupt IMP for at least 2 weeks Close observation ²	Down-titration: interrupt IMP for at least 2 weeks Close observation ²	Discontinue IMP ²	Discontinue IMP ²
After at least 2 weeks	AST and ALT <3xULN		AST or ALT ≥3xULN		
	Re-escalate to next dose level for at least 2 weeks Weekly LFTs for the first 2 weeks (biweekly for the following weeks, or more frequently at investigator’s discretion) Repeat re-escalation to next higher dose level every 2 weeks (or longer at investigator’s discretion) if AST and ALT <3xULN		Discontinue IMP Report SAE and complete liver event page for any of abnormalities listed below ³ : 
 - AST/ALT increase ≥8xULN - AST/ALT increase ≥3xULN with signs of severe liver damage¹ 		

¹ Signs of severe liver damage:

- total bilirubin ≥1.5xULN OR international normalized ratio >1.5, and/or
- symptoms: appearance of fatigue, nausea, vomiting, right upper abdominal quadrant pain or tenderness, fever, rash and/or eosinophilia (>5%)

² Close observation recommendations:

- Monitor two to three times per week all of the following parameters: ALT, AST, alkaline phosphatase, total bilirubin, eosinophils, INR. If local regulations allow, home visits can be performed if subjects cannot come to the clinical study center.
- Frequency of retesting can be reduced to once a week or less if abnormalities stabilize or the IMP has been discontinued; however, monitoring might still be needed more frequently taking into consideration the standard of care and/or changes to this.
- Based upon Investigator’s discretion gastroenterology or hepatology consultations, additional serology testing, imaging and pathology assessments may be required
- Re-query history of symptoms, prior and concurrent diseases, concomitant medication and non-prescription medicines, herbal, dietary supplements, alcohol use, recreational drug use, special diets.

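### For AST/ALT of 3 to 8xULN without signs of severe liver damage, Protocol 4.1.2 asks for fewer initial retests than Appendix 9 and leaves INR off its list; its 8xULN boundary also differs from the rest of the protocol

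*Protocol*

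**What the plan says.** Protocol 4.1.2 applies from Visit 4 onwards. At 3 to 5xULN with no sign of severe liver damage, the investigator either reduces to the low dose or interrupts IMP for two weeks or more. At 5 to 8xULN, IMP is interrupted. For both bands the monitoring instruction is "Re-test AST, ALT, alkaline phosphatase, total bilirubin, and eosinophils within 48 to 72 hours, approximately at 7 days, thereafter approximately at 14 days", and the sentence continues "and also assess signs of severe liver damage". Those signs are defined further down in 4.1.2 and include INR above 1.5.

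Section 4.1.2 also defines close observation, a heavier package: the same five analytes plus INR, two or three times weekly, with a search for other causes. It attaches this only to two discontinuation rules, of which one reads "AST or ALT >8xULN: permanently discontinue IMP with close observation"; the other covers 3xULN or more with signs of severe liver damage.

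The section opens by pointing elsewhere: "For abnormal liver function tests (LFTs), specific guidance is described in Appendix 9". In that appendix the 3 to 5xULN cell reads "reduce or interrupt IMP for at least 2 weeks Close observation", and the 5 to 8xULN cell also carries close observation. The footnote says: "Monitor two to three times per week all of the following parameters: ALT, AST, alkaline phosphatase, total bilirubin, eosinophils, INR". It then allows relief: "Frequency of retesting can be reduced to once a week or less if abnormalities stabilize or the IMP has been discontinued".

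For the top boundary, 4.5.4 (discontinuation), 9.1.5 (SAE reporting) and Appendix 9 (both) all use 8xULN or above.

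**The concern.** Two parts of one protocol give different monitoring for the same subjects, and the body text is the lighter of the two at the start. A site working from 4.1.2 would schedule three retests and order five analytes.

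The missing INR matters most. Three laboratory findings count as signs of severe liver damage: eosinophilia, raised total bilirubin and raised INR. The retest list names the first two and omits only the third. The close-observation panel in the same section is the same list with INR added, so a reader comparing the two could take the omission as intended. Yet AST or ALT of 3xULN or more with INR above 1.5 means permanent discontinuation and an SAE report. In the 3 to 5xULN band the subject may still be taking IMP at the reduced dose while the retests are done.

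The boundary mismatch is smaller but of the same kind: at one value, 4.1.2 gives a different instruction from the section that governs discontinuation.

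**Working it through.** This is a comparison of texts with a short count. The plan states no figure to reproduce.

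**Retests in the first 14 days**

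- Section 4.1.2: one at 48 to 72 hours, one at about day 7, one at about day 14. Total 3.
- Appendix 9 without reduction: 2 × 2 = 4 to 3 × 2 = 6. Difference from 4.1.2: 4 − 3 = 1 to 6 − 3 = 3.
- Appendix 9 reduced to weekly after week 1: 2 + 1 = 3 to 3 + 1 = 4. Difference: 0 to 1.
- Appendix 9 with no test in week 2 (its wording allows less than weekly): 2 to 3. Difference: −1 to 0.

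**Analytes**

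| | 4.1.2 retest list | 4.1.2 close observation | Appendix 9 close observation |
|---|---|---|---|
| AST, ALT, alkaline phosphatase, total bilirubin, eosinophils | named | named | named |
| INR | not named | named | named |
| Applies to 3–8xULN without signs | yes | no | yes |

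**Could routine sampling supply the INR?** Protocol 6.6.2 includes INR in the routine coagulation panel. Planned visit days (Protocol 4.1) give these gaps:

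- Week 2 to 4: 14 days
- Week 4 to 8 and Week 8 to 12: 28 days each
- Week 12 to 18: 42 days
- Week 18 to 26, 26 to 34 and 34 to 42: 56 days each
- Week 42 to 52: 70 days
- after Week 52: 84 days

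When a scheduled visit detects the elevation, only the Week 2 to Week 4 gap brings a routine INR at about the third retest. From Week 4 on, every planned gap exceeds 14 days. The shortest under the ordinary windows in Protocol 6.1 is Week 8 to Week 12, 28 − 4 − 4 = 20 days.

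**A value of exactly 8.0xULN**

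- Section 4.1.2: not above 8, so it falls in the 5 to 8xULN band. IMP is interrupted for at least two weeks and may be re-escalated once AST and ALT are below 3xULN.
- Section 4.5.4 and Appendix 9: IMP is discontinued.
- Section 9.1.5 and Appendix 9: an SAE is reported.

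Neighbouring bullets in the 4.1.2 list keep the ≥ sign, so a reading error from the PDF is unlikely to explain the plain >.

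**The case against.** The strongest reply is that INR is already required. The retest sentence also asks for the signs of severe liver damage to be assessed, and INR above 1.5 is one of them, so the assessment cannot be completed without an INR. That is right as far as it goes: INR is implied and only its name is missing. But a sentence that names two of the three laboratory signs and leaves the third to a footnote invites the omission.

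Second, the visit that reveals the elevation normally includes an INR, and Protocol 6.6.2 lets the investigator order additional tests. This covers the initial classification. It does not cover a rise in INR during the following two weeks, which is what the retests are for.

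Third, 4.1.2 sends the reader to Appendix 9, the two schedules can be met together, and Appendix 9 calls its own schedule recommendations. A site that follows both is safe; the problem lies with a site that follows 4.1.2 alone. The permitted reduction narrows the gap and can reverse it, as the count shows, but only once values have stabilised or IMP has been discontinued. The initial schedule in 4.1.2 is still the lighter one.

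Fourth, 4.5.4 makes discontinuation mandatory at 8xULN, and the SAP liver categories (9.4.2.9) use the same boundary, so the > in 4.1.2 looks like a slip. It probably is one, and its reach is a single value. That argues for correcting it.

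**Conclusion.** The concern holds on all three parts, from current protocol text. For AST or ALT of 3 to 8xULN without signs of severe liver damage, 4.1.2 asks for 3 retests in two weeks against 4 to 6 under Appendix 9. The shortfall is 1 to 3 tests with no reduction, and 0 to 1 if Appendix 9 testing becomes weekly after the first week. INR is implied in 4.1.2 but not named in the list that a site would order from. The investigation of other causes that belongs to close observation is likewise attached to these bands in Appendix 9 and not in 4.1.2. The boundary mismatch affects only exactly 8.0xULN.

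The count assumes that Appendix 9 testing starts at the stated frequency and that the elevation is found at a scheduled visit on its planned day. The documents give no expected number of subjects in these bands, so the total effect cannot be sized. No efficacy endpoint or analysis is touched; this is a subject-safety inconsistency in the protocol as written and should be corrected.

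**What to change.** Three edits in Protocol 4.1.2:

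1. Add INR by name to the retest list for the 3 to 8xULN bands.
2. Apply the Appendix 9 close-observation schedule to those bands, and keep the 48-to-72-hour, 7-day and 14-day retests as a minimum. Keeping that minimum prevents the permitted reduction from taking testing below what 4.1.2 requires now.
3. Change >8xULN to ≥8xULN in the discontinuation rule.

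The cost is the text change plus about 1 to 3 extra blood tests per affected subject in the first two weeks, or 0 to 1 if values are stable and testing becomes weekly after week 1. Appendix 9 already recommends these tests.
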